### 11.2.6 Notification

# 11.2.6.1 Serious Adverse Events

The investigator or designee must report all SAEs promptly to within 24 hours of first becoming aware of the event by completing, signing, and dating the SAE pages, verifying the accuracy of the information recorded on the SAE pages with the corresponding source documents and eCRF, and sending the SAE pages to the Pharmacovigilance Department by one of the following methods:

- Email:
- FAX number:

The written report should be submitted on the SAE form provided for this purpose. At the time of first notification, the investigator or designee should provide the following information, if available:

- Protocol number.
- Reporter (study site and investigator).
- Subject's study number.
- Subject's year of birth.
- Subject's gender.
- Date of first dose of IP.
- Date of last dose of IP, if applicable.
- Adverse event term
- Date of occurrence of the event.
- A brief description of the event, outcome to date, and any actions taken.
- The seriousness criteria(on) that were met.
- Concomitant medication at onset of the event.
- Relevant past history information.
- Relevant laboratory test findings.
- Investigator's opinion of the relationship to IP(s) ("Is there a reasonable possibility that the IP caused the SAE? Yes or No?").
- Whether and when the investigator was unblinded as to the subject's treatment assignment.

Any missing or additional relevant information concerning the SAE should be provided to the recipient(s) of the initial information as soon as possible on a follow-up SAE Report Form together with the following information: AE, date of occurrence, subject ID, study ID, IP, and site number. This will allow the follow-up information to be linked to the initial SAE report.

Specific information may be requested by the Pharmacovigilance Department using a follow up request form. The investigator is required to comply with applicable regulations (including local laws and guidances) regarding the notification of his/her health authorities, institutional review boards (IRBs), principal and coordinating investigators, study investigators, and institutions.

### 11.2.6.2 Non-serious Adverse Events

Nonserious AEs will be recorded in the eCRF and reported by

## 11.3 Special Considerations

# 11.3.1 Adverse Events of Special Interest

The following events will be considered as AEs of special interest during this study:

- Psychosis.
- Suicidal ideation.

Based on the population under study, and their age, suicidal ideation will be considered as an AE of special interest.

# 11.3.2 Pregnancy

All women of childbearing potential who participate in the study should be counseled on the need to practice adequate birth control and on the importance of avoiding pregnancy during study participation. Women should be instructed to contact the investigator or study staff immediately if pregnancy occurs or is suspected.

Pregnancy testing will be conducted prior to administration of IP on every woman of childbearing potential. A woman who is found to be pregnant at the Screening Visit will be excluded from the study and considered to be a screening failure.

A woman who becomes pregnant during IP treatment or within 30 days of discontinuing the IP will be immediately discontinued from study participation. The investigator must report the pregnancy within 24 hours of learning of the pregnancy to Pharmacovigilance using the Pregnancy Data Collection Form via the same fax and email address as for SAE reporting. The investigator should contact the designated individual(s) who receive SAE notification and record information related to the pregnancy on an Exposure in Utero form/other designated form provided by the sponsor or its designee.

Early Termination Visit assessments are required as soon as possible after learning of the pregnancy. The investigator is also responsible for following the pregnancy until delivery or termination. These findings must be reported on the Exposure in Utero Form/other designated form and forwarded to the designated individual(s). The event meets the SAE criterion only if it results in a spontaneous abortion or a congenital anomaly.

### 12. DATA SAFETY MONITORING BOARD

No Data Safety Monitoring Board will be required.

### 13. STATISTICS

# 13.1 Study Endpoints

# 13.1.1 Primary Efficacy Endpoint

The primary endpoint for the assessment of efficacy will be the ADHD-RS-5 score. The analysis will be based on changes from the baseline value and will test the hypothesis that there is no difference between the treatments (ie, that the difference is 0) against a 2-tailed alternative.

Version: Final Version v4.0 Page 42 of 58

# 13.1.2 Secondary Efficacy Endpoints

Secondary endpoints will include the CGI-I, CGI-S, and other assessment scales. Further exploratory analyses will examine the effect of covariates such as dose-level and age. All quantitative endpoints will be described with traditional summary statistics and tabulated by treatment group and visit.

# 13.1.3 Safety Endpoints

Adverse events will be coded using the most recent version of the Medical Dictionary for Regulatory Affairs (MedDRA) and tabulated by system organ class and preferred term. Adverse events will be analyzed by frequency, severity, relationship to IP, and their effect on participation in the study.

Clinical laboratory values will be compared to normal ranges and flagged for levels of clinical concern. The analysis will focus on the frequencies of abnormal values as well as within-subject changes observed during the course of the study.

Vital signs and ECG recordings will also be examined for changes during the study that may be attributed to exposure to IP.

The C-SSRS will also be examined for changes that may be attributed to exposure to IP.

# 13.2 Sample Size Determination

Enrollment of 90 subjects is expected to yield 80 subjects who complete the study as planned. Assuming an effect size of 0.7, this number will provide approximately 90% power to detect a significant difference between the treatments based on a 2-tailed  $\alpha = 0.05$  comparison of mean change from Baseline.

# 13.3 Analysis Populations

The design of this study yields 3 main populations of scientific interest.

The Safety Population will consist of all subjects who are randomized into the study and receive any amount of IP.

The Intent-to-Treat (ITT) Population will be composed of all subjects who are randomized into the study.

The occurrence of significant protocol deviations may lead to the exclusion of some subjects from specific analyses, thereby yielding a Per-protocol (PP) Population.

Specific subgroups of these populations may also be evaluated as warranted by the experimental results.

Membership in the analysis populations will be determined prior to unblinding.

# 13.4 Statistical Analyses

This section presents a summary of the planned statistical analyses. Additional details regarding data handling, analytical methods, and presentation of results will be found in the Statistical Analysis Plan for this study. The Statistical Analysis Plan will be finalized prior to database lock.

### 13.4.1 Study Subjects and Demographics

# 13.4.1.1 Disposition and Withdrawals

The disposition of all subjects enrolled in this study will be fully described with respect to their randomization status and ultimate discontinuation. Subjects who discontinue the study will be summarized with the reason for discontinuation.

### 13.4.1.2 Protocol Deviations

All subject data will be reviewed for the occurrence of protocol deviations. Prior to database lock, all protocol deviations will be reviewed in a blinded fashion and classified with respect to the potential to influence experimental outcomes. The results of this review may lead to enumeration of a PP Population, as described in Section 13.3.

# 13.4.1.3 Demographics and Other Baseline Characteristics

The analysis of demographic and baseline data will be performed for all study populations.

Demographic variables include age, gender, race, ethnicity, height, and weight. Baseline subject characteristics to be summarized will include medical history, physical examination, ECG assessment, C-SSRS evaluation, an IQ test (WASI-II), and clinical laboratory tests.

Prior and concomitant medications will be summarized by treatment group and by the number and percentage of subjects taking each medication. Medications will be coded according to the World Health Organization Drug Dictionary (WHO-DD) Anatomical Therapeutic Chemical (ATC) classes and preferred terms.

# 13.4.2 Exposure and Compliance

Exposure to IP will be summarized for all participating subjects. Subjects will be described with respect to cumulative exposure as well as categorized by the highest dose received.

Compliance with study medication will be determined for each subject. Based on capsule counts, the number of doses administered will be expressed as the proportion of doses scheduled. Compliance will be assessed independently for each phase of the study (ie, dose optimization and maintenance).

# 13.4.3 Efficacy Analyses

All efficacy measures will be described with standard summary statistics. Continuous variables will be summarized by N, mean, and standard deviation, and categorical variables by the number and percent of subjects in each category. Where appropriate, estimates will be presented with 95% confidence intervals.

Efficacy analyses will attempt to quantify the effects of treatment with NFC-1 relative to placebo. The null hypothesis of no difference between active and placebo will be tested against a 2-tailed alternative with a type-I error rate of 0.05.

# 13.4.3.1 Primary Analysis

The primary analysis will focus on the effect of treatment on ADHD, as indicated by the ADHD-RS-5. The change in ADHD-RS-5 will be derived as the difference between the last post-treatment value and that recorded at the Baseline visit. The analysis of the change will employ a 1-way analysis of variance (ANOVA) model with a term for treatment (active or placebo). Depending on the fit of the single-factor model, subsequent exploratory analyses may be performed that include additional independent factors (eg, age, gender, and/or maintenance dose of study drug) as well as covariates that have been determined to be associated with experimental results (eg, baseline value of the dependent variable). Results of these exploratory analyses will be presented as estimates for all factors included in the model with corresponding 95% confidence intervals and associated levels of statistical significance.

This analysis will be performed with primary focus on the ITT Population.

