#### 9.9 Dose Adjustment Criteria

The duration of the dose-optimization period is 4 weeks to allow for up-titration to the highest dose and no more than one down-titration to the previous dose, if necessary.

Subjects will be instructed to take NFC-1 or placebo each morning upon awakening (at 7:00 a.m. to 9:00 a.m.) and in the mid-afternoon (3:00 p.m. to 5:00 p.m.). On Day 1, all subjects will begin taking NFC-1 or placebo and will be evaluated after 7 days ( $\pm$  2 days) for tolerability and effectiveness. Subjects may be titrated weekly to the next available dose strength after 7 days ( $\pm$  2 days) on the previous dose, based on the overall response of the subject. Additionally, if needed, a subject may be down-titrated to the previous dose level in order to optimize tolerability and efficacy. Subject response will be categorized by the investigator as 1 of 3 conditions and associated actions, with titration continuing until an "acceptable response" is achieved. These conditions are defined as follows:

Intolerable response (ie, intolerable side effects): Requires the subject to be tapered to a lower dose of NFC-1 (if available). However, if this lower dose produces an intolerable response as well, the subject should be discontinued from the study.

Ineffective response: The subject is not showing a significant reduction in symptoms, and requires increasing titration of NFC-1 to the next available dose strength, provided tolerability is acceptable, followed by weekly evaluation.

Acceptable response: A response is defined as acceptable if it shows a significant reduction in symptoms with tolerable side effects. Subjects categorized as "acceptable" may be maintained at their current dose for the remainder of the optimization period. Subjects who are tolerating study medication at the highest available dose but do not achieve an acceptable response should continue in the trial at that dose.

Further, if the "acceptable" dose is well tolerated and, in the opinion of the investigator, the subject would potentially receive additional symptom reduction, the dose may be increased to the next higher dose level.

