## 13.4.3.2 Secondary Analyses

Secondary efficacy analyses will examine the effects of the treatment on changes observed in other efficacy measures (ie, CGI-S, ASHS, and SCARED). These analyses will model the overall or total scale scores and will employ the same general approach as for the primary analysis. All secondary efficacy measures will be treated as continuous measurement scales and analyzed by the ANOVA methods described above.

Results of the CGI-I assessment will also be dichotomized and presented for each week of treatment. CGI-I scores of 1 or 2 will be combined into a single group labelled "Improved" and scores of 3 to 7 will be combined and labelled "No Improvement." The observed proportions of "Improved" subjects will be compared between treatment groups at each week of the study.

In addition, analysis of the weekly results from ADHD-RS-5 and CGI-I will be evaluated for evidence of trend over time. This analysis will employ a linear mixed-effects model with repeated measures on each subject. Terms for the model will be selected as described for the primary analysis.

Secondary analyses will focus on the ITT Population. However, analyses of the PP Population may be performed if warranted by the data.

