2.1.2 Study Endpoints

The primary endpoint for the assessment of efficacy will be the Attention Deficit Hyperactivity Disorder Rating Scale Version 5 (ADHD-RS-5) score. The analysis will be based on the changes from the baseline value and will test the hypothesis that there is no difference between the treatments (i.e., that the difference is 0) against a 2-tailed alternative.

SAP FINAL Version 2.0

Additionally, secondary endpoints of efficacy will include the CGI-I, CGI-S, ASHS, SCARED scales, and Response and Remission criteria using the ADHD-RS-5 and CGI-I [4]. Further analyses will examine effect of gender and dose level. All quantitative endpoints will be described with traditional summary statistics and tabulated by treatment group and visit.

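### Exploratory efficacy models may include maintenance dose, which titration sets from the subject's own response, so neither a dose p-value nor a dose-adjusted treatment effect can be interpreted

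*Protocol*

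**What the plan says.** **Models.** The protocol's primary model (13.4.3.1) has treatment only. Depending on how it fits, later exploratory models may add "additional independent factors (eg, age, gender, and/or maintenance dose of study drug"). The reporting rule is "Results of these exploratory analyses will be presented as estimates for all factors included in the model", each with a 95% confidence interval and significance level. The Synopsis repeats the dose example. For the mixed model of weekly ADHD-RS-5 and CGI-I results, 13.4.3.2 says "Terms for the model will be selected as described for the primary analysis".

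**Firmer statements.** Protocol 13.1.2: "Further exploratory analyses will examine the effect of covariates such as dose-level and age". SAP 2.1.2: "Further analyses will examine effect of gender and dose level". Neither names a model. SAP Section 10, which lists departures from the protocol, does not withdraw the dose factor.

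**How dose is set.** In Protocol 9.9 an ineffective response is defined as follows: "The subject is not showing a significant reduction in symptoms, and requires increasing titration of NFC-1 to the next available dose strength". A subject with an acceptable response may stay on the current dose, or may go up if it is well tolerated and the investigator expects further benefit. An intolerable response leads down. Visit 5 is the last titration visit. Placebo comes in the same three nominal levels (9.1), so every subject in either arm carries a nominal dose.

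**Not stated.** The documents do not say how dose is coded for placebo subjects in a model, or that dose groups are not randomised groups.

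**The concern.** Maintenance dose is partly a record of the early outcome. Subjects who do badly in Weeks 1 to 3 are moved up, in both arms, and outcomes within a subject are correlated over time. A dose coefficient at Week 6 then largely asks whether poor early responders are still poor responders, and it can differ from zero when dose does nothing. The problem is sharpest in the weekly mixed model, where the Week 1 to 3 outcomes both determine the dose and are part of what is modelled. Protocol 10.3.2.2 also says the CGI assessment guides dosing, and CGI-I is one of that model's outcomes.

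The treatment term suffers as well. Once dose is in the model, the arms are compared at equal dose, which means conditioning on something treatment may have changed.

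At stake are the secondary messages of a Phase 2 trial: a false, usually inverse, dose-response that could misdirect dose selection, and an adjusted treatment effect that could be quoted for or against the robustness of the primary result.

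**Working it through.** **1. The plan's own figure.** Protocol 13.2: "Assuming an effect size of 0.7, this number will provide approximately 90% power to detect a significant difference". Protocol 13.4.3 has the null "tested against a 2-tailed alternative with a type-I error rate of 0.05". With SD 1, power = Φ(0.7 × √(n/2) − 1.96).
- n = 45 per arm (90 enrolled): Φ(3.320 − 1.960) = Φ(1.360) = 91.3% (90.7% with the t distribution).
- n = 40 per arm (80 completers): Φ(3.130 − 1.960) = Φ(1.170) = 87.9% (87.1% with t).

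The stated 90% is reproduced with 45 per arm.

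**2. Simulation set-up.** 40 per arm, 3,000 trials per scenario, three titration decisions (Visits 3, 4, 5), least squares on change from baseline. Assumptions not in the documents:
- SD of change 11 (so 0.7 SD = 7.7 points); baseline mean 38, SD 6.5, floor at the entry limit of 28; placebo change −5 to −10.
- Between-visit correlation ρ from 0.3 to 0.7.
- 5% intolerance at the 200 mg step (10% in the q = 0.9 runs).
- An adequate response is a 30% fall. Section 9.9 gives no number, so this borrows the responder cut-off in SAP 8.2.
- q is the probability that an acceptable responder is also escalated.

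Without dose in the model, the treatment test rejects in 4.6-5.6% of null trials. At 0.7 SD it gives an unbiased estimate (about −7.7) with 87-88% power.

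**3. Dose test with no drug effect** (nominal dose in both arms, 2 df, nominal level 5%):

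| | ρ = 0.3 | ρ = 0.5 | ρ = 0.7 |
|---|---|---|---|
| q = 0 | 45% | 90% | 99.5% |
| q = 0.5 | 22% | 50% | 81% |
| q = 0.9 | not run | 7% | not run |
| dose assigned at random | not run | 4.5% | not run |

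The random-dose control shows that the titration rule causes the excess. A separate simulation with 45 per arm gave 75-100%, 28-88% and about 8-11% for the same three escalation practices. Together the ranges are about 45-100%, 22-88% and 7-11%.

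At ρ = 0.5, q = 0 and no drug effect, the NFC-1 dose groups differ from all placebo by −5.1 (100 mg), −1.6 (200 mg) and +4.3 points (400 mg). That is a false inverse dose-response.

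**4. Dose-adjusted treatment effect, true value −7.7.**

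*(a) Nominal dose coded in both arms.* The estimates at ρ = 0.3 / 0.5 / 0.7 are −6.9 / −6.6 / −6.3 (q = 0) and −7.4 / −7.2 / −7.0 (q = 0.5), about 4-19% toward zero. The 45-per-arm simulation gave a larger shift, from 0.70 to 0.44-0.54 SD. With more intolerance on drug (25% against 3%; ρ = 0.5, q = 0) the estimate is −4.8 and power falls from 88% to 48%.

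*(b) Placebo coded 0 mg, linear in dose.* Here adjusted effect = unadjusted effect − slope × mean active dose, because the treatment term extrapolates the active arm to 0 mg. At ρ = 0.5, q = 0:
- Active-arm shares at 100, 200 and 400 mg are 0.426, 0.243 and 0.331. Mean dose in units of 100 mg = 0.426 + 2 × 0.243 + 4 × 0.331 = 2.236.
- Slope is +3.400 points per 100 mg.
- −7.684 − 3.400 × 2.236 = −15.29, against −15.28 from the fitted models.

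Across ρ the estimates are −12.5 / −15.3 / −18.0 (q = 0) and −11.4 / −13.8 / −16.4 (q = 0.5). With no drug effect, the treatment test rejects in 23% / 52% / 78% (q = 0) and 14% / 27% / 48% (q = 0.5) of trials.

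*(c) Placebo as its own category*, as in the SAP by-dose table shells. The treatment indicator equals the sum of the three active-dose indicators. Treatment and dose are aliased, and no single dose-adjusted treatment effect exists.

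**The case against.** **These models are optional and exploratory, and the SAP mostly avoids them.** This is largely right. Section 13.4.3.1 says may and gives dose only as an example. The SAP 8.1 ANCOVA has treatment and baseline score only. SAP Section 8 and the table index contain no weekly mixed model, no efficacy p-value for dose and no dose-adjusted treatment effect. The by-dose efficacy tables are descriptive. A reader might infer from SAP 4.2, which says planned analyses will be performed, that the dose model is mandatory. It is not: 4.2 does not turn an optional model into a required one. What remains is that Protocol 13.1.2 and SAP 2.1.2 both say dose level will be examined, the only model route on paper is the one in 13.4.3.1, and Section 10 does not close it. An exploratory label does not repair conditioning on early response.

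**The size depends on escalation practice.** This stands. Section 9.9 allows acceptable responders to be escalated, which weakens the link between non-response and dose. The documents do not say how often that would happen. A reader might infer that a spurious dose effect is close to certain, but at q = 0.9 the test is near its nominal level.

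**The direction of bias is not fixed.** This also stands. A reader might infer that adjusting for dose always understates the drug effect. That holds only when nominal dose is coded in both arms, and the documents do not define the coding. Under that coding with equal tolerability the treatment test also keeps its size (4-5% under the null), so its p-value is not invalid in every version. With no efficacy but more intolerance on drug (25% against 3%), it rejected in 14% of trials with an estimate of +2.1 points.

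**Conclusion.** The concern holds for the exploratory dose models. Because 9.9 makes dose a result of response and tolerability, a p-value for dose cannot be read as evidence about dose. With no drug or dose effect it rejects in about 45-100% of trials if only non-responders escalate, about 22-88% if half of acceptable responders do too, and about 7-11% if almost all do. A dose-adjusted treatment effect is biased toward zero, biased away from zero, or not estimable, according to a placebo coding that neither document defines. The mechanism follows from the protocol text. The sizes rest on assumed visit correlations, response threshold, escalation practice and intolerance rates.

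A reader might infer that the primary result is at risk. The documents do not support that: neither the protocol's ANOVA nor the SAP's ANCOVA contains dose. The descriptive by-dose tables are also sound as descriptions, provided they are not read as randomised comparisons.

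**What to change.** In SAP 2.1.2, replace the sentence on gender and dose level with text that:
- limits terms in any efficacy model to variables fixed before randomisation (baseline score, age, gender);
- states that dose is reported descriptively only, with no dose p-value and no dose-adjusted treatment effect.

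Add a footnote to the by-dose efficacy tables (14.2.1.2, 14.2.2.3, 14.2.3.3) that dose groups result from titration and are not randomised comparisons. In SAP Section 10, record that this supersedes the dose factor in the Protocol Synopsis, 13.1.2, 13.4.3.1 and, through its term selection, 13.4.3.2. Align the protocol text at the next amendment. Protocol 14.8 requires a formal amendment with IRB approval for any protocol change, so the SAP should carry the correction meanwhile.

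The cost is a few sentences and a footnote, with no new data and no change to the primary test. What is lost is an exploratory dose p-value that the titration design cannot support.
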